5.6.1 Extent of Exposure

Study treatment exposure (such as treatment duration, total dose received, and dose modifications) will be summarized with descriptive statistics.

Exposure to study drug (number of study drug administrations and duration of treatment), regardless of SC or IV administration, will be summarized by treatment group in the safety-evaluable population.

Exposure will also be summarized by the administration route (SC vs. IV).

If a participant did not resume treatment after a treatment discontinuation, then the duration of treatment is the time from first study drug to the earlier of:

- Date of treatment discontinuation or date of study treatment completion in Study Period A
- The analysis cutoff date

Otherwise, if a participant resumed treatment after a treatment discontinuation, then the duration is the summation of duration of each treatment period, where the duration of the first treatment period is defined as the time from first study drug to the date of first treatment discontinuation and the duration of the last treatment period is defined as the time from the last treatment resumption date to the earlier of:

- Date of treatment discontinuation or date of study treatment completion in Study Period A
- The analysis cutoff date

The duration of the rest of the treatment periods is defined as the time from the treatment resumption date to the date of treatment discontinuation.

See Section [5.7.4](#) for PK/PD analyses.

5.6.2 Adverse Events

All treatment-emergent adverse events, serious adverse events, adverse events leading to death, protocol-specified adverse events of special interest (including amyloid-related imaging abnormalities—edema/effusion [ARIA-E], amyloid-related imaging abnormalities— hemosiderin deposition [ARIA-H], cerebral macrohemorrhages, pneumonia, *potential drug-induced liver injury, and suspected transmission of infectious agents by the investigational product*) and adverse events leading to study treatment discontinuation will be summarized by MedDRA Preferred Term, appropriate thesaurus level by treatment arm. Adverse events will be summarized by severity and by relationship to study drug. For events of varying severity, the highest grade will be used in the summaries.

In addition, treatment-emergent injection reactions, infusion-related reactions and COVID-19 infections will be summarized by treatment group.

Only treatment-emergent adverse events will be included in the analyses, defined as any adverse event reported during or after the first dose of study drug. Adverse events with a missing onset date will be considered to be treatment-emergent. Adverse events with a partially missing onset date will also be included as treatment-emergent if the month (if it was recorded) and the year occur on or later than the month and year of the study treatment start date.

A separate listing of adverse events reported during the screening period (before the first dose of study drug) will also be produced.

5.6.3 Clinical Laboratory Data

Clinical laboratory data (serum chemistry, hematology evaluations, including CBC with differential and platelet counts, and urinalysis values) will be summarized over time by descriptive statistics by treatment group, with grades identified where appropriate. Additionally, a shift table of selected laboratory tests will be used to summarize the baseline and maximum post-baseline severity grade.

5.6.4 MRI Evaluations

Neuroradiologic evaluation with respect to the occurrence of cerebral vasogenic edema (ARIA-E); superficial siderosis of the CNS or cerebral microhemorrhages (ARIA-H); or of cerebral macrohemorrhages will be performed during the *Study Period A* treatment period and will be summarized by treatment group using descriptive statistics.

5.6.5 Vital Signs

Vital signs (pulse rate, blood pressure, body temperature, and respiratory rate) will be displayed over time and changes from baseline will be summarized by treatment group.

5.6.6 Electrocardiograms

Electrocardiogram data will be displayed over time and changes from baseline for relevant ECG intervals will be summarized by treatment group *up to Week 17*.

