3.2.2 Rationale for Crenezumab Dosage

In this Phase II study, crenezumab 720 mg SC Q2W was selected as the dose and dosing regimen, following the results of the Phase II studies in sporadic AD; this dose provides similar exposures as the 15 mg/kg IV Q4W dose in Phase II that suggested a trend for efficacy in sporadic AD dementia. This SC dose has been administered in this study since August 2015 and has so far been well-tolerated. Since July 2019, a higher dose of 60 mg/kg IV Q4W is being offered to study participants as this is assumed to have a higher potential for efficacy and was also being investigated in Phase III studies in sporadic AD.

The Phase III studies (BN29552 [CREAD] and BN29553 [CREAD 2]) in patients with prodromal or mild (sporadic) AD tested a 4-fold higher dose (i.e., 60 mg/kg IV Q4W) of crenezumab than in Phase II compared with placebo. Based on results from a preplanned interim analysis of Study BN29552 assessing the safety and efficacy of crenezumab indicating that Study BN29552 was unlikely to meet its primary endpoint of change from baseline in CDR-SOB score, both Phase III studies were discontinued.

Study GN28352 continues given that this at-risk ADAD population differs from the sporadic prodromal to mild AD population in the following ways: the population is much younger, clinically asymptomatic at study entry, and carries a mutation that is specifically linked to amyloid metabolism. Approximately half of the carrier participants have been reported to have negative amyloid PET scans at baseline (Reiman et al. 2018). In addition, this *PSEN1 E280A* mutation is reported to be associated with an increased rate of amyloid accumulation in brain, as measured by amyloid PET compared with sporadic AD (Fleisher et al. 2015), suggesting the potential for crenezumab in delaying the progression of amyloid pathology may provide greater benefit in this patient population compared with sporadic AD. Furthermore, a quantitative systems pharmacology model of AD has been developed by Genentech and calibrated to both the ADAD (*PSEN1 E280A* mutation) and sporadic AD populations. Simulations from this model predict that both the 720 mg SC Q2W and 60 mg/kg IV crenezumab Q4W dosing regimens will delay the progression of amyloid

accumulation in the brain in the ADAD population, as measured by amyloid PET standard uptake ratio, with a greater effect associated with the 60 mg/kg IV Q4W regimen (internal data).

[figure not shown]

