4.10.4.2 Clinical Laboratory Evaluations

Clinical laboratory data (serum chemistry, hematology evaluations, including complete blood count with differential and platelet counts, and urinalysis values) and ECG data will be summarized over time by descriptive statistics by treatment group.

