4.10.4.5 Electrocardiogram

Electrocardiogram data and changes from baseline for relevant ECG intervals will be summarized by treatment group.

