5.6 SAFETY ANALYSES

All safety analyses of Study Period A will be performed in the safety-evaluable population (see Section 4 for definition).

As the study participants are considered treatment-exposed during the 16-week (approximately 5 half-lives) follow-up period, adverse events reported within 16 weeks after the last dose of study drug administered in Study Period A will be included in the safety analyses from Study Period A (contrary to the description in the protocol stating they will be summarized separately). At the end of Study Period B, safety analyses on

Study Period A will be refreshed (*due to the additional 16-week safety follow-up data accrued in Period A after the primary analysis*) and reported in the final CSR.

Adverse events reported within 16 weeks after the last dose of study drug administered in Study Period B will be included in the safety analyses on Study Period B.

Safety analyses of Study Period B and/or of the potential OLE data are summarized in Section 5.10.2.

Safety will be assessed through summaries of exposure to study treatment, adverse events, changes in laboratory test results, MRI findings, changes in vital signs and ECGs, and changes in suicidality assessment.

Study treatment exposure (such as treatment duration, total dose received, and dose modifications) will be summarized with descriptive statistics.

All verbatim adverse event terms will be mapped to MedDRA thesaurus terms, and adverse event severity will be graded according to National Cancer Institute Common Terminology Criteria for Adverse Events (NCI CTCAE), v4.0. All adverse events, serious adverse events, adverse events leading to death, adverse events of special interest, and adverse events leading to study treatment discontinuation that occur on or after the first dose of study treatment (i.e., treatment-emergent adverse events) will be summarized. All adverse events will be summarized by severity and by relationship to study drug. For events of varying severity, the highest grade will be used in the summaries.

Relevant laboratory, vital signs (pulse rate, respiratory rate, blood pressure, pulse oximetry, and temperature), and ECG data will be displayed by time, with grades identified where appropriate. Additionally, a shift table of selected laboratory tests will be used to summarize the baseline and maximum post-baseline severity grade.

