Changes in vital signs and ECGs will be summarized. Proportion of participants with suicidal ideation or behavior, as reported in the suicidality assessment, will be analyzed by treatment groups.

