5.10.2 Safety Analyses

If the Sponsor decides *to terminate the study based on the primary analysis results from Study Period A*, then safety data from Study Period B will be reported in the final CSR. The Study Period B safety population is defined in the beginning of Section 5.10.

If the Sponsor decides *to extend Study Period B or initiate an OLE, then safety data from Study Period B will be reported in the final CSR and safety data from the OLE will be summarized in the OLE CSR*. The OLE safety population is defined in the beginning of Section 5.10.

All the safety analyses described in Section 5.6 will be reported.

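### SAP 5.6.6 stops the by-group summary of ECG interval change at Week 17 without a reason, so it contains no scheduled ECG on the 60 mg/kg IV dose

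*SAP*

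**What the plan says.** SAP Section 5.6.6 has two parts. First, "Electrocardiogram data will be displayed over time", with no week limit attached to that clause. Then come the changes from baseline, where "relevant ECG intervals will be summarized by treatment group *up to Week 17".

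The general text of SAP Section 5.6 sets no limit on either part: "and ECG data will be displayed by time, with grades identified where appropriate", and "Changes in vital signs and ECGs will be summarized".

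The protocol sets none either. Section 4.10.4.5 reads "Electrocardiogram data and changes from baseline for relevant ECG intervals will be summarized by treatment group", and Section 4.10.4.2 states that "ECG data will be summarized over time by descriptive statistics by treatment group".

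On dosing, Protocol Section 3.2.2 records "Since July 2019, a higher dose of 60 mg/kg IV Q4W is being offered to study participants", and Section 3.1 puts the IV exposure at roughly four times that of SC dosing. For Period B, SAP Section 5.10.2 says "All the safety analyses described in Section 5.6 will be reported" and does not single out ECGs.

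**The concern.** SAP Section 1 gives the SAP precedence over the protocol's analysis plan, so the Week 17 limit would govern if the SAP is followed as written. The trial takes ECGs for years after Week 17, and IV dosing starts later than that. The planned comparison of interval change between arms would then describe early SC dosing only.

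At stake is whether the report contains a by-group summary of ECG change at the higher exposure and over long-term treatment. A display of values over time does not replace a summary of change by arm. The same question arises in Period B, where carriers formerly on placebo receive crenezumab for the first time.

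The limit carries no explanation. By contrast, SAP Section 5.6.8 does give a rationale for analysing only part of the anti-drug antibody data.

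**Working it through.** The documents give no figure to reproduce. The check sets the Week 17 limit against the ECG rows of the flowcharts.

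**Inputs**
- Sent to the central ECG vendor (Protocol 4.5.1.4): baseline, Week 4 and Week 12 for all participants. Substudy participants also have Week 16 and Week 17, the latter 7 days after the Week 16 dose.
- SC schedule to Week 104 (Protocol Appendix 1): after baseline, Weeks 4, 12, 24, 52 and 104, plus Week 16 and the visit 7 days later for the substudy.
- IV schedule (Protocol Appendices 3 and 4): Weeks 24, 52, 104, 156, 208, 260, 312, 364 and 416, plus the ET-A or ET-B visit.
- Period B schedule (Protocol Appendices 5 and 6): Weeks 53, 105 and 157, every 52 weeks after that, and the early termination/safety follow-up visit 16 weeks after the last dose.
- Reading: the footnotes to Appendices 1 to 4 say that routine ECGs are calculated and read locally.

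**Counts of scheduled post-baseline ECGs**

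| Setting | At or before Week 17 | After Week 17 |
|---|---|---|
| SC, outside substudy, through Week 104 | 2 (W4, W12) | 3 (W24, W52, W104) |
| Same, through Week 260* | 2 of 8 = 25% | 6 of 8 = 75% |
| Substudy, through Week 260* | 4 of 10 = 40% | 6 of 10 = 60% |
| IV flowchart, through Week 416 | 0 of 9 | 9 of 9 |
| Period B treatment visits | 0 | all, first at Week 53 |

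*The SC ECG row after Week 104 is missing from the text available for review. These two rows assume that it matches the IV schedule (Weeks 156, 208 and 260). The first row needs no such assumption.

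The limit covers 17/260 = 6.5% of the minimum treatment period. Outside the substudy, the last ECG inside the limit is Week 12.

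**Comparison of the texts**
- Protocol 4.10.4.2 and 4.10.4.5 and SAP 5.6 agree with one another: no limit. SAP 5.6.6 alone has one.
- SAP Appendix 1 lists two departures from the protocol: the Period B safety population and the adverse events of the 16-week follow-up. The ECG limit is not among them. That list is written against Protocol Version 10, and the comparison here is with Version 11.
- Week 17 coincides with the last centrally submitted ECG. The SAP does not give this as the reason.

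**The case against.** The strongest defence is that the limit is a sound choice left unexplained. Interval changes are best analysed on standardised central readings, and these end at Week 17. Later tracings are read locally, paper copies are filed at the site, and the documents do not show that interval values from them are in the database. This stands as a reason to keep the central analysis to Week 17 and to present later ECGs separately. It does not by itself justify having no summary of them, given the unlimited wording elsewhere.

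A reader might infer that all ECGs on IV dosing are left out of the safety analysis, or that ECG safety at the higher exposure goes unassessed. The documents do not support that. The limit most naturally attaches to the summary of change, although the sentence leaves some doubt about whether the display also stops at Week 17. SAP 5.6 repeats the display without a limit. Investigators must review every tracing, adverse events are summarised without a week limit (SAP 5.6.2), and the iDMC reviews unblinded safety data in Period A.

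A reader might also infer that Period B ECGs are excluded and that their table would be empty. That too goes beyond the text. Week 17 is a Period A visit, and Period B restarts at its own Week 1. SAP 5.10.2 carries the Section 5.6 analyses over without excluding ECGs. Even on a literal carry-over, someone who stopped after the Week 1 dose would have a follow-up ECG at about Week 1 + 16 = Week 17. What stands is that the SAP does not say how the limit applies.

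**Conclusion.** The point holds as an unexplained conflict with a real consequence. If SAP 5.6.6 is followed, the by-group summary of interval change contains none of the 9 scheduled visit ECGs on the IV flowchart and no scheduled ECG from Week 24 onward. Through Week 104, 3 of 5 post-baseline ECGs on the SC schedule outside the substudy fall out. Through Week 260 it is 6 of 8, if the SC schedule matches the IV schedule after Week 104.

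The finding does not reach further than that. ECG data are still to be displayed over time, and the position in Period B is unclear rather than excluded. That the limit follows from central reading is plausible but is an inference. The Appendix 1 omission assumes that Version 10 of the protocol also set no limit. The efficacy conclusions are not affected. The SAP should be corrected because the gap falls on the higher exposure and on long-term treatment.

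**What to change.** Amend the SAP as follows.

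1. In Section 5.6.6, state that the Week 17 limit applies only to the centrally read interval analysis, and give the reason. State that the display over time has no such limit.
2. Add a separate descriptive summary of the locally read ECGs after Week 17, by arm, with SC and IV periods shown. Use interval changes from baseline where these were recorded, and otherwise the proportion of participants with a clinically significant abnormality.
3. In Section 5.10.2, state that the Week 17 limit does not carry into Period B and that ECGs there are summarised by treatment received.
4. List the departure from Protocol 4.10.4.2 and 4.10.4.5 in SAP Appendix 1.

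The cost is a few descriptive tables from ECGs the trial already takes, with no new procedures. Local readings are less standardised than central ones. If interval values are not in the database, only the categorical summary is possible, and that needs an abnormality field whose presence the documents do not confirm. The switch to IV was the participant's choice after randomisation, so the SC and IV periods should be described and not tested against each other. Placebo was given by the same routes, so each route still has its own comparator arm.

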5.6.7 Suicidal Ideation and Behavior

The proportion of participants with suicidal ideation or behavior, as reported in the suicidality assessment, will be analyzed by treatment group.

5.6.8 Anti-Drug Antibodies

The number and percentage of participants with confirmed positive anti-drug antibodies (ADAs) will be reported for each treatment group at baseline (prevalence of ADAs in the crenezumab and placebo groups) and after treatment with crenezumab (treatment-emergent ADAs). *At the primary analysis, the Sponsor will have only analyzed partial ADA data. If the study is negative and results from the partial ADA data are consistent with the extensive ADA data collected in previous Phase I-III studies, no additional ADA analyses are planned. The rationale is that ADA data from approximately 1900 samples that have already been tested is sufficient to confirm the low immunogenicity risk of crenezumab in this population without impacting the interpretation of the overall study results. However, if the study is positive, (at least one of the primary endpoints is statistically significant) the Sponsor will then analyze the complete ADA dataset in the final analysis and report it.*

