1.2.2.3 Immunogenicity

The immunogenicity of crenezumab was assessed in the completed Phase I, Phase II, and Phase III Studies ABE4427g, ABE4662g, ABE4869g, ABE4955g, GN28525, GP29172, GP29523, GN29632, GP40201, and BN29552.

In the two Studies GN29632 and BN29552 in patients with sporadic AD, the same dose of 60 mg/kg BW was investigated as in this study, with the following findings:

- Study GN29632: anti-drug antibody (ADA) incidence was 0% (0 of 75 patients)
- Study BN29552: The incidence of ADAs was 0.5% with 2 of 397 patients exposed to crenezumab having transient ADAs throughout the study. In these 2 patients, the presence of ADAs did not appear to have an effect on the exposure to crenezumab, based on PK data.

See the Crenezumab Investigator's Brochure for additional details on nonclinical and clinical studies.

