4.5.1.8 Immunogenicity Sampling

Blood samples will be collected to assess the possible development of ADAs in all participants as noted in the Study Flowchart (see [Appendix 1](#), [Appendix 2](#), [Appendix 3](#), and [Appendix 4](#)) and in case of anaphylaxis, anaphylactoid, or serious hypersensitivity reactions. In addition, for any participant suspected of developing anaphylaxis, anaphylactoid, or serious hypersensitivity reactions warranting discontinuation of dosing, an ADA sample and a concurrent PK sample must be collected as close as possible to the event, and then at the 4-week end of treatment visit and at the 16-week safety follow-up visit after the final dose. Serum samples will be analyzed for antibodies to crenezumab using a bridging ELISA. Samples may be tested for antibodies against other drug product substances.

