4.10.4.6 Anti-Drug Antibodies

The number and percentage of participants with confirmed positive ADAs will be reported for each treatment group.

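### SAP 5.6.8 lets a negative trial call low ADA risk confirmed from a sample count, with no participant denominator or confidence limit behind the conclusion

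*SAP*

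**What the plan says.** Protocol 4.5.1.8 samples everyone: "Blood samples will be collected to assess the possible development of ADAs in all participants". Protocol 4.10.4.6 sets the summary per participant and attaches no efficacy condition: "The number and percentage of participants with confirmed positive ADAs will be reported for each treatment group". SAP 5.6.8 opens with the same per-participant summary, at baseline and after treatment.

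SAP 5.6.8 then says that only part of the ADA data will have been analysed at the primary analysis. What follows depends on the efficacy result:

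- **Negative study.** If "results from the partial ADA data are consistent with the extensive ADA data collected in previous Phase I-III studies, no additional ADA analyses are planned". SAP 5.6.8 justifies this as follows: "ADA data from approximately 1900 samples that have already been tested is sufficient to confirm the low immunogenicity risk of crenezumab in this population".
- **Positive study.** "the Sponsor will then analyze the complete ADA dataset in the final analysis and report it".

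For the earlier data, Protocol 1.2.2.3 lists ten studies but gives figures only for the two at the same 60 mg/kg dose. In GN29632, "anti-drug antibody (ADA) incidence was 0% (0 of 75 patients"). In BN29552, "The incidence of ADAs was 0.5% with 2 of 397 patients exposed to crenezumab having transient ADAs throughout the study". For further detail it points to the Investigator's Brochure.

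**The concern.** To say that low risk is confirmed is to make a positive claim, and such a claim needs a bound. The SAP gives none. It does not define what counts as consistent, gives no upper limit, and does not state how many exposed participants lie behind the samples. As written, the absence of a visible difference from earlier studies is enough.

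The support offered is a count of samples, whereas the precision of a per-participant incidence depends on the number of crenezumab-treated participants tested. Repeat draws from one person help to find a positive in that person, but they do not add people. Draws from placebo participants say nothing about treatment-emergent ADA.

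The claim is also about this particular population, which Protocol 3.2.2 describes as differing from sporadic AD: much younger, asymptomatic at entry and carrying the mutation. A negative trial report could state the risk as confirmed low when the trial's own data could not exclude an incidence several times the earlier figure.

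**Working it through.** **Inputs**

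- Reference incidence: 2 of 397 (Protocol 1.2.2.3, study BN29552).
- Crenezumab participants: 84. This is an assumption, taken from the SAP Appendix 2 simulation that mimics this study. Range used: 63 (84 × 0.75, the 25% dropout in Protocol 4.10.8) to 100 (the planned arm size).
- Samples tested: about 1900 (SAP 5.6.8), with no split by arm, person or visit.
- Criterion for consistent: none in the documents. Fisher's exact test at 0.05 against 2/397 is used as a stand-in.

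**Step 1. Reproduce the reference.** 2/397 = 0.504%, which rounds to the stated 0.5%. Its own exact 95% interval is 0.06% to 1.81%.

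**Step 2. What zero positives would exclude.** With 0 of N positive, the exact upper limit is 1 − 0.025^(1/N) two-sided and 1 − 0.05^(1/N) one-sided.

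| N | Two-sided 95% limit | One-sided 95% limit |
|---|---|---|
| 63 | 5.7% | 4.6% |
| 84 | 4.3% | 3.5% |
| 100 | 3.6% | 3.0% |

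At N = 84 the ratios to the reference are 4.3/0.504 = 8.5 and 3.5/0.504 = 6.9. One positive of 84 would give a two-sided upper limit of 6.5%.

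**Step 3. How often a real rise would pass as consistent.** Against 2/397, Fisher's two-sided p is 0.14 for 2 of 84 and 0.039 for 3 of 84, so up to 2 positives pass. The miss probability is P(X ≤ 2) for X ~ Binomial(84, fold × 0.504%). For N = 63 the cutoff is the same; for N = 100, 4 positives are needed, so up to 3 pass.

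| True rise | Incidence | Missed, N = 84 | Missed, N = 63 | Missed, N = 100 |
|---|---|---|---|---|
| 4-fold | 2.0% | 76% | 87% | 86% |
| 6-fold | 3.0% | 53% | 70% | 64% |
| 8-fold | 4.0% | 34% | 53% | 42% |
| 10-fold | 5.0% | 20% | 38% | 25% |

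**Step 4. What the 1900 samples could be.** The flowcharts (Protocol Appendices 1 to 4) schedule ADA draws at baseline and Weeks 24, 52, 76, 104, 128, 156, 180, 208, 232 and 260, which is 11. There are 6 more to Week 416, making 17, and early termination and follow-up bring the most to about 19.

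- Crenezumab arm only: 1900/84 = 22.6 per person, more than can be scheduled. On the 84 assumption the set therefore very likely includes placebo draws.
- Both carrier arms: 11 × 168 = 1848, so 1900 would be roughly the whole schedule to Week 260.
- All 252 recruited (Protocol 3.2): 11 × 252 = 2772, so 1900 is 69% of the draws to Week 260.

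The documents do not say which of the last two applies, or whether it is something else.

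**The case against.** Much of the case for leaving the section alone is fair.

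- **Reporting is already per participant.** The sample count appears only in the rationale and is never used as a denominator. This stands; the fault lies in the sufficiency argument, not in the planned table.
- **The test is not the SAP's.** Safety comparisons here are descriptive, and no rule in the SAP would pass 2 of 84 automatically. This stands, so the miss rates are illustrative. The upper limits in Step 2 need no such rule.
- **The SAP leans on all earlier Phase I–III data.** Most of those figures are in the Investigator's Brochure, so the fold-changes rest on the one non-zero figure the protocol gives. This stands as a limit on the ratios. The absolute limit of 4.3% does not depend on it.
- **Consequences are watched elsewhere.** Event-driven ADA and PK samples, injection and infusion reactions and serum troughs are covered whatever the efficacy result, and the shortcut is pre-specified for the negative branch only. This stands, and it keeps the point minor.

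Two stronger readings are tempting and are not supported. A reader might infer that any 4- to 10-fold rise would usually be missed. Under the stand-in rule that is true at 4-fold, about even at 6-fold and false at 10-fold, which is detected about 80% of the time at N = 84 and 62% at N = 63. A reader might also infer that the reported incidence must be biased low. Transient ADAs, like the two in BN29552, could be missed if the partial set omits some of a participant's scheduled draws, but its make-up is not given and Step 4 shows it could be nearly complete to Week 260.

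**Conclusion.** The point holds as a minor one. In the negative-study branch, SAP 5.6.8 permits a conclusion that low immunogenicity is confirmed in this population without stating the number of exposed participants, a confidence limit or a criterion for agreement. With about 84 crenezumab participants all tested, even zero positives leaves incidences up to 4.3% (two-sided) open, about 8 times the 0.5% reference. Fewer tested participants would widen that limit.

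The result rests on the assumed 84 and on 2/397 as the benchmark; the miss rates rest in addition on a Fisher rule that the SAP does not contain. The finding concerns what may be concluded, not evidence that immunogenicity is in fact higher.

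**What to change.** In SAP 5.6.8, replace the rationale based on the number of samples with a statement along these lines:

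- Treatment-emergent ADA incidence is reported as x/N, where N is the number of crenezumab-treated participants with at least one tested post-baseline sample, with an exact 95% confidence interval, overall and for participants sampled on IV dosing.
- This is done whether the efficacy result is positive or negative.
- The share of scheduled crenezumab-arm ADA samples that were tested is reported alongside.
- Any statement of low immunogenicity is expressed through the upper confidence limit, not as confirmed. If the sponsor wants a margin, it should be chosen and justified in advance.

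No margin is proposed here, because the documents give no basis for one and a tight choice has a price. At N = 84, for example, a rule that fails on a single positive would withhold the conclusion 1 − (1 − 2/397)^84 = 35% of the time even if the true rate equalled the reference.

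The cost is a wording change and one exact interval, with no new patients, visits or mandatory assays. The immunogenicity statement becomes slightly less favourable. Reporting the share tested discloses any gap in coverage but does not close it.
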